7.2 Study Population

7.2.1 Subject Disposition

The total number of subjects enrolled (treated or not treated) will be presented along with the reason for not being treated. This analysis will be performed on the all enrolled subjects population.

Number of subjects who discontinued study treatment along with corresponding reason will be tabulated by treatment group. Reason for discontinuation will be derived from subject status CRF page. This analysis will be performed only on the all treated subjects.

Number of subjects who discontinued study follow-up along with corresponding reason will be tabulated by treatment group. Reason for discontinuation will be derived from subject status CRF page. This analysis will be performed only on the all subjects entered follow-up population.

A by-subject listing for all enrolled subjects will also be provided, showing whether the subject was treated along with the reason for not being treated.

A by-subject listing for all treated subjects will be provided showing the subject's off treatment date and whether the subject continue in the treatment period/study along with the reason for going off treatment period/study.

A by-subject listing for subjects entered follow-up will be provided showing the subject's off study date and the reason for not continuing in follow-up.

7.2.2 Demographics and Other Baseline Disease Characteristics

The following demographic and baseline disease characteristics will be summarized and listed:

- Age (continuous)
- Age categorization (< 65, ≥ 65 and < 75, ≥ 75 and < 85, ≥ 85, ≥ 75, ≥ 65)
- Sex (Male vs. Female)
- Race (White, Black or African American, Asian, Other)
- Ethnicity (Hispanic/Latino and Not Hispanic/Latino)

- Disease stage at initial diagnosis
- Disease stage at study entry
- ECOG performance status
- Number of prior systemic cancer therapy regimens (0, 1, 2, 3, ≥ 4 , not reported)

7.3 Extent of Exposure

7.3.1 Administration of Study Therapy

Duration of study therapy for both nivolumab and daratumumab will be summarized in days (descriptive statistics). Subjects also will be categorized based on the duration of study therapy: 1-28, 29-56, 57-84, 85-168, more than 169 days.

The number and percentage of NSCLC patients who discontinued daratumumab and continued with single agent treatment of nivolumab as a result of the BMS decision communicated to investigators after 13-June-2018 will be summarized.

7.4 Efficacy

Analyses of progression free survival (PFS) and objective response rate (ORR) will be based on the Investigator evaluation.

CI's for endpoints will be at the two-sided 95% level. P-values will not be reported. Point estimates and confidence bounds for efficacy variables will be rounded to the second decimal place.

7.4.1 Analysis of Objective Response Rate and Disease Control Rate

One of the objectives of the study is to estimate the ORR per Investigator among all treated subjects.

The number and percentage of subjects in each category of BOR per Investigator (complete response [CR], partial response [PR], stable disease [SD], progressive disease [PD], or unable to determine [UTD]) will be presented. Estimates of response rate and disease control rate, along with its exact two-sided 95% CI by Clopper and Pearson³ will be presented.

7.4.2 Duration of Response

Duration of response (DOR) will be evaluated for subjects who achieved PR or CR. The DOR will be estimated using the Kaplan-Meier (KM) product limit method and will be displayed graphically. The plot will also present number of events, number of subjects involved, medians, and 95% CI's for the medians. Median values of DOR, along with two-sided 95% CI in each treatment group will be computed based on a log-log transformation method.

7.4.3 Analysis of Progression-Free Survival

One of the objectives of the study is to estimate the progression-free survival (as determined by Investigator) for all treated subjects.

The PFS function for each tumor type will be estimated using the KM product limit method and will be displayed graphically. A two-sided 95% CI for median PFS will be computed via the log-log transformation method.

7.5 Safety

7.5.1 Deaths

A by-subject listing of deaths will be provided for all enrolled subjects population.

7.5.2 Serious Adverse Events

Serious adverse events will be summarized for all treated subjects:

- Overall summary of SAEs by worst CTC grade (any grade, grade 3-4, grade 5) presented by SOC/PT.
- The analysis will be conducted using the 30-day safety window.

A by-subject SAE listing will be provided for the “enrolled subjects” population.

7.5.3 Adverse Events Leading to Discontinuation of Study Therapy

AEs leading to discontinuation will be summarized:

- Overall summary of AEs leading to discontinuation by worst CTC grade (any grade, grade 3-4, grade 5) presented by SOC/PT.

The analysis will be conducted using the 30-day safety window.

A by-subject AEs leading to discontinuation listing will be provided.

7.5.4 Adverse Events

Adverse events will be summarized.

The following analyses will be conducted using the 30 days safety window only:

- Overall summary of any AEs by worst CTC grade (1, 2, 3, 4, 5, not reported, total) presented by SOC/PT.
- Overall summary of any AEs presented by worst CTC grade (1, 2, 3, 4, 5, not reported, total) by SOC/PT. This table will be restricted to events with an incidence greater or equal to 5% in any treatment group.

A by-subject AE listing will be provided.

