**Table 2.-3: Follow-up Procedural Outline (CA2099GW)**

	Local Lab (LL) or Central Lab (CL)	Day 30, 100 Follow-up (±1 wk)	Notes
Performance Status (ECOG)		X	See Appendix 5 for ECOG scale.
Physical Examination		X	Targeted physical examination, include weight. Must include the following body systems: cardiovascular, gastrointestinal, pulmonary
Vital Signs		X	Includes body temperature, respiratory rate, and seated blood pressure and heart rate. Blood pressure and heart rate must be measured after the participant has been resting quietly for at least 5 minutes.
			
Adverse Events Assessment		X	NSAEs and SAEs must be collected up to 100 days after study drug discontinuation.
Laboratory Tests			
Pregnancy Test	LL	X	
CBC with Differential and Platelets	LL	X	To be done at Follow-up 1. To be repeated at Follow-up 2 if study related toxicity persists.
Serum Chemistry	LL	X	Chemistry panel includes LDH, AST, ALT, ALP, albumin, total bilirubin, BUN or serum urea level, creatinine, Ca, Mg, Na, K, Cl, glucose, phosphate, carbon dioxide or bicarbonate. Amylase and lipase: only for participants with pancreatic adenocarcinoma. To be done at Follow-up 1. To be repeated at Follow-up 2 if study related toxicity persists.
Thyroid Function Tests	LL	X	TSH (reflex to free T3 and free T4 if abnormal result).

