### 3) Age and Reproductive Status

- a) Males and Females,  $\geq 18$  years of age
- b) Women of childbearing potential (WOCBP) must have a negative serum or urine pregnancy test (minimum sensitivity 25 IU/L or equivalent units of HCG) within 24 hours prior to the start of study treatment.
- c) Women must not be breastfeeding
- d) WOCBP must agree to follow instructions for method(s) of contraception from the time of enrollment for the duration of treatment with study drug(s) plus approximately 5 half-lives of study drug(s) plus 30 days (duration of ovulatory cycle) for a total of 5 months post treatment completion.
- e) Males who are sexually active with WOCBP must agree to follow instructions for method(s) of contraception for the duration of treatment with study drug(s) plus approximately 5 half-lives of study drug(s) plus 90 days (duration of sperm turnover) for a total of 7 months post-treatment completion.
- f) WOCBP who are continuously not heterosexually active are also exempt from contraceptive requirements and still must undergo pregnancy testing as described.

Investigators shall counsel WOCBP and male participants who are sexually active with WOCBP on the importance of pregnancy prevention and the implications of an unexpected pregnancy. Investigators shall advise WOCBP and male participants who are sexually active with WOCBP on the use of highly effective methods of contraception. Highly effective methods of contraception have a failure rate of  $< 1\%$  when used consistently and correctly.

At a minimum, participants must agree to the use one highly effective method of contraception as listed in [Appendix 4](#).

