- Isolated Grade 4 electrolyte imbalances/abnormalities that are not associated with clinical sequelae and are corrected with supplementation/appropriate management within 72 hours of their onset
- Any event that leads to delay in dosing lasting > 8 weeks from the previous dose requires discontinuation, with the following exceptions:
  - Dosing delays to allow for prolonged steroid tapers to manage drug-related AEs are allowed.
  - Dosing delays lasting > 8 weeks from the previous dose that occur for non-drug-related reasons may be allowed if approved by the BMS medical monitor.
- Any adverse event, laboratory abnormality, or intercurrent illness which, in the judgment of the Investigator, presents a substantial clinical risk to the participant with continued study drug dosing.

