6 STUDY PERIODS, TREATMENT REGIMENS AND POPULATIONS FOR ANALYSES

6.1 Study Periods

- Baseline period:
 - Baseline evaluations or events will be defined as evaluations or events that occur before the date and time of the first dose of study treatment. Evaluations (laboratory test) on the same date and time of the first dose of study treatment will be considered as baseline evaluations. Events (AEs) on the same date and time of the first dose of study treatment will not be considered as pre-treatment events.
 - In cases where the time (onset time of event or evaluation time and dosing time) is missing or not collected, the following definitions will apply:
 - ◆ Pre-treatment AEs will be defined as AEs with an onset date prior to but not including the day of the first dose of study treatment;
 - ◆ Baseline evaluations (laboratory tests) will be defined as evaluations with a date on or prior to the day of first dose of study treatment.
- Post baseline period:
 - On-treatment AEs will be defined as AEs with an onset date and time on or after the date and time of the first dose of study treatment (or with an onset date on or after the day of first dose of study treatment if time is not collected or is missing). For subjects who are off study treatment, AEs will be included if event occurred within a safety window of 30 days (or 100 days depending on the analysis) after the last dose of study treatment. No “subtracting rule” will be applied when an AE occurs both pre-treatment and post-treatment with the same preferred term and grade.
 - On-treatment evaluations (laboratory tests) will be defined as evaluations taken after the day (and time, if collected and not missing) of first dose of study treatment. For subjects who are off study treatment, evaluations should be within a safety window of 30 days (or 100 days depending on the analysis) after the last dose of study treatment.

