7.5.5 Laboratory Parameters

The analysis population for each laboratory test is restricted to treated subjects meeting that laboratory test abnormality.

A summary as worst CTC grade on-treatment per subject and a by-subject listing of the following laboratory parameters abnormalities will be provided: hemoglobin, hematocrit, leukocytes, platelet count, ALT, AST, alkaline phosphatase (ALP), total bilirubin, lactate dehydrogenase, blood urea nitrogen (BUN) or serum urea level, creatinine, sodium, potassium, calcium, chloride, magnesium, creatinine clearance (CLcr), carbon dioxide or bicarbonate, amylase, glucose, phosphate, albumin, urinalysis labs, serology tests, FSH and lipase.

A summary and a by-subject listing of the following thyroid specific abnormalities will be provided: TSH, FT3, FT4.

A by-subject listing of differences in categorization of SI and US laboratory test results will be provided.

The analyses will be conducted using the 30-day safety window.

In addition, further analyses on specific laboratory parameters will be performed by treatment group:

Abnormal Hepatic Function Test

The number of subjects with the following laboratory abnormalities from on-treatment evaluations will be summarized:

- ALT or AST > 3 x ULN, > 5 x ULN, > 10 x ULN and > 20 x ULN
- Total bilirubin > 2 x ULN
- ALP > 1.5 x ULN
- Concurrent (within 1 day) ALT or AST > 3 x ULN and total bilirubin > 1.5 x ULN
- Concurrent (within 30 days) ALT or AST > 3 x ULN and total bilirubin > 1.5 x ULN
- Concurrent (within 1 day) ALT or AST > 3 x ULN and total bilirubin > 2 x ULN
- Concurrent (within 30 days) ALT or AST > 3 x ULN and total bilirubin > 2 x ULN

Abnormal Thyroid Function Test

The number of subjects with the following laboratory abnormalities from on-treatment evaluations will be summarized:

- TSH value > ULN and
 - with baseline TSH value \leq ULN
 - with at least one FT3/FT4 test value < LLN within 2-week window after the abnormal TSH test
 - with all FT3/FT4 test values \geq LLN within 2-week window after the abnormal TSH test
 - with FT3/FT4 missing within 2-week window after the abnormal TSH test.
- TSH < LLN and
 - with baseline TSH value \geq LLN
 - with at least one FT3/FT4 test value > ULN within 2-week window after the abnormal TSH test
 - with all FT3/FT4 test values \leq ULN within 2-week window after the abnormal TSH test
 - with FT3/FT4 missing within 2-week window after the abnormal TSH test

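### The SAP's AE, SAE, AE-discontinuation and main laboratory tables stop 30 days after last dose, although the protocol collects AEs and SAEs to 100 days and sets no 30-day limit on its primary endpoint

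*SAP*

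**What the plan says.** SAP 6.1 leaves the post-treatment window open: "AEs will be included if event occurred within a safety window of 30 days (or 100 days depending on the analysis) after the last dose". The same choice is given there for laboratory evaluations. The analysis sections then settle it as follows.

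- SAP 7.5.4 (all AEs): "The following analyses will be conducted using the 30 days safety window only".
- SAP 7.5.3 (AEs leading to discontinuation): "The analysis will be conducted using the 30-day safety window". SAP 7.5.2 says the same for SAEs.
- SAP 7.5.5 (laboratory worst grade, and the basic TSH, FT3 and FT4 summary): "The analyses will be conducted using the 30-day safety window".
- SAP 7.5.5, further hepatic and thyroid function summaries: "laboratory abnormalities from on-treatment evaluations will be summarized". No window is restated for these.

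No analysis in the SAP is assigned 100 days. The by-subject listings in 7.5.1 to 7.5.4 state no window.

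The protocol collects for longer. Table 2.-3 says: "NSAEs and SAEs must be collected up to 100 days after study drug discontinuation". Section 9.2.1 sets the same period for non-serious and serious events. Table 4.-1 defines the primary endpoint as incidence of AEs, SAEs and specific laboratory abnormalities by worst grade, without a time limit. Section 10.3.2 plans to tabulate all on-study AEs and SAEs and mentions no 30-day cut.

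**The concern.** Tolerability is the primary objective, and its endpoint is an incidence. The plan collects post-treatment events for 100 days but reports rates on the first 30 and gives no reason for the narrowing. This is a single-arm trial, so each cohort's safety message is its own incidence table, with no control group against which a shortened window might even out.

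Two further places deserve attention.

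- **Discontinuation table.** SAP 7.1.1 defines an AE leading to discontinuation by the action taken with study drug and sets no time limit. SAP 7.5.3 then adds a 30-day limit. Because the protocol permits long gaps between doses, an event can end treatment more than 30 days after the last dose.
- **Follow-up 1 laboratory tests.** The visit tolerance extends past Day 30, so a result can be on schedule for the protocol and outside the window for the SAP.

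**Working it through.** **1. The plan's own safety figure.** SAP section 5 gives a probability above 87% of seeing an event with a 5% rate in 40 participants. The chance of at least one case is 1 − (1 − 0.05)^40 = 0.8715, so the figure reproduces.

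**2. What a shorter window does to that figure.** Take 5% as the rate over the whole collection period. Let f be the share of affected participants whose event starts only after Day 30. The documents give no f, so a range is shown. The tables then see a rate of 0.05 × (1 − f), and the detection probability is 1 − [1 − 0.05(1 − f)]^40.

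| f (assumed) | Rate seen in tables | Probability of at least one case in 40 |
|---|---|---|
| 0% | 5.00% | 0.8715 |
| 5% | 4.75% | 0.8572 |
| 10% | 4.50% | 0.8415 |
| 20% | 4.00% | 0.8046 |
| 30% | 3.50% | 0.7595 |
| 50% | 2.50% | 0.6368 |

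The stated 87% needs a rate of at least 1 − 0.13^(1/40) = 4.973%, so it fails once f exceeds 1 − 4.973/5, about 0.5%.

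**3. Calendar coverage.** 100 − 30 = 70 post-treatment days are collected for AEs and SAEs but enter no incidence table in SAP 7.5. This counts days, not events.

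**4. Holds that end in discontinuation.** The SAP 6.1 window runs from the last dose of study treatment, so the relevant gap is since the last dose of either drug. The protocol's limits leave these days beyond Day 30:

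- Nivolumab, 8 weeks from the previous dose (8.1.1: "Any event that leads to delay in dosing lasting > 8 weeks from the previous dose requires discontinuation, with the following exceptions"): 56 − 30 = 26 days, and longer under the listed exceptions.
- Daratumumab on the 4-weekly schedule, with its 21-day dosing window (7.1.2): 28 + 21 = 49, and 49 − 30 = 19 days.
- Daratumumab 6-week hold from Week 25 (7.1.2, 8.1.2): 42 − 30 = 12 days if counted from the last dose. If counted from the missed 4-weekly dose, 28 + 42 = 70, and 70 − 30 = 40 days.
- Delay unrelated to study therapy, up to 84 days (8.1.2): 84 − 30 = 54 days.

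A new AE with onset in those days that ends treatment meets the definition in SAP 7.1.1 but can fall outside the table in SAP 7.5.3. The calculation requires that neither drug is given again.

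**5. Follow-up 1 laboratory tests.** Table 2.-3 places the visit at Day 30 ± 1 week, which is Days 23 to 37. Results on Days 31 to 37 are on schedule and outside a 30-day window. The first on-study TSH is at Week 8 (Table 2.-2). For a participant who stops before then, Follow-up 1 can therefore be the only scheduled post-baseline thyroid test.

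**The case against.** The case for leaving the plan alone has several sound parts.

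- **A 30-day main table is defensible.** The AE tables are all-causality. In advanced cancer, Days 31-100 also contain events from progression and subsequent therapy. SAP section 10 says version 2.0 serves a close-out synoptic report focused on key safety and efficacy. This supports keeping the 30-day tables. It does not explain why the 100-day option in SAP 6.1 is never used.
- **The listings.** A reader might infer that late toxicity disappears from the report. The documents do not support that, because the AE, SAE, AE-discontinuation and death listings state no window. A listing, however, gives no incidence, and incidence is the endpoint.
- **Not every laboratory summary is fixed at 30 days.** The further hepatic and thyroid summaries say only that they use on-treatment evaluations, which SAP 6.1 allows to mean 30 or 100 days. Thirty days is the natural reading, but the accurate criticism is that the window is unstated. The AE summaries by ADA status in SAP 7.6 are silent as well.
- **Most AEs that cause a hold are still counted.** Such an AE will usually start before the next due dose, inside 30 days. AEs during a hold that ends in re-dosing also count, and continuing one drug restarts the clock. It is also unclear whether the cut-off, worded for participants already off treatment, reaches back into a hold.
- **Late laboratory loss is small.** CBC, chemistry and thyroid tests are repeated at Follow-up 2 only if study-related toxicity persists, so such toxicity has usually appeared earlier.
- **Calendar and exposure figures do not measure lost events.** It is tempting to read 70 of 100 days as 70% of late safety data. It is equally tempting to read 7 of the 15 permitted Follow-up 1 days as nearly half the visits. Nothing shows that events or visits are spread evenly. Nor does residual drug give an event rate. The contraception rule ("approximately 5 half-lives of study drug(s) plus 30 days (duration of ovulatory cycle) for a total of 5 months post treatment completion") implies a half-life of about (5 − 1) × 30.4375 / 5 = 24.35 days. Under simple exponential decline, about 43% would remain at Day 30 and 6% at Day 100. That makes a look beyond Day 30 reasonable, but it is one approximate value for two antibodies.

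**Conclusion.** The gap is real and should be closed. The SAP reports the primary endpoint's AE and SAE incidences on 30 days only, while the protocol collects 100 days and sets no 30-day limit. AEs and SAEs starting on Days 31-100 enter no incidence table in SAP 7.5. Two narrower faults accompany this. A new AE that ends treatment more than 30 days after the last dose of either drug can be left out of the discontinuation table, against the SAP's own definition. On-schedule Follow-up 1 laboratory results on Days 31-37 fall outside the window.

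The size cannot be established from the documents. The fall in detection probability from 87% to about 84% or 76% rests on assuming f of 10% or 30%. It also applies to a cohort of 40, a target that NSCLC did not reach. A reader might go further and conclude that the tables must systematically understate toxicity. That is not shown, because some late events will reflect progression or later therapy.

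**What to change.** In the SAP:

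1. Keep the 30-day tables in 7.5.2 to 7.5.5. Beside them, add AE, SAE, AE-leading-to-discontinuation, hepatic and thyroid summaries on the 100-day window that 6.1 already allows.
2. In 7.5.3, count every AE from the treatment phase, including dose holds, whose recorded action is discontinuation of study drug, whatever the gap since last dose. Say how the window applies when a hold precedes discontinuation.
3. In 7.5.5, state the window for the further hepatic and thyroid summaries.
4. In 7.5.5, let on-schedule Follow-up 1 laboratory results through Day 37 count in the 30-day laboratory tables. This matters most for hematology and general chemistry, for which no 100-day version is proposed.

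The cost is SAP wording and a second run of existing table programs on data already collected. No visit, sample or clinical rule changes. The downside is that the 100-day tables will include some events from progression or subsequent therapy, which is why both windows should be shown side by side.

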7.5.5 Laboratory Parameters

The analysis population for each laboratory test is restricted to treated subjects meeting that laboratory test abnormality.

A summary as worst CTC grade on-treatment per subject and a by-subject listing of the following laboratory parameters abnormalities will be provided: hemoglobin, hematocrit, leukocytes, platelet count, ALT, AST, alkaline phosphatase (ALP), total bilirubin, lactate dehydrogenase, blood urea nitrogen (BUN) or serum urea level, creatinine, sodium, potassium, calcium, chloride, magnesium, creatinine clearance (CLcr), carbon dioxide or bicarbonate, amylase, glucose, phosphate, albumin, urinalysis labs, serology tests, FSH and lipase.

A summary and a by-subject listing of the following thyroid specific abnormalities will be provided: TSH, FT3, FT4.

A by-subject listing of differences in categorization of SI and US laboratory test results will be provided.

The analyses will be conducted using the 30-day safety window.

In addition, further analyses on specific laboratory parameters will be performed by treatment group:

Abnormal Hepatic Function Test

The number of subjects with the following laboratory abnormalities from on-treatment evaluations will be summarized:

- ALT or AST > 3 x ULN, > 5 x ULN, > 10 x ULN and > 20 x ULN
- Total bilirubin > 2 x ULN
- ALP > 1.5 x ULN
- Concurrent (within 1 day) ALT or AST > 3 x ULN and total bilirubin > 1.5 x ULN
- Concurrent (within 30 days) ALT or AST > 3 x ULN and total bilirubin > 1.5 x ULN
- Concurrent (within 1 day) ALT or AST > 3 x ULN and total bilirubin > 2 x ULN
- Concurrent (within 30 days) ALT or AST > 3 x ULN and total bilirubin > 2 x ULN

Abnormal Thyroid Function Test

The number of subjects with the following laboratory abnormalities from on-treatment evaluations will be summarized:

- TSH value > ULN and
 - with baseline TSH value \leq ULN
 - with at least one FT3/FT4 test value < LLN within 2-week window after the abnormal TSH test
 - with all FT3/FT4 test values \geq LLN within 2-week window after the abnormal TSH test
 - with FT3/FT4 missing within 2-week window after the abnormal TSH test.
- TSH < LLN and
 - with baseline TSH value \geq LLN
 - with at least one FT3/FT4 test value > ULN within 2-week window after the abnormal TSH test
 - with all FT3/FT4 test values \leq ULN within 2-week window after the abnormal TSH test
 - with FT3/FT4 missing within 2-week window after the abnormal TSH test

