**4. OBJECTIVES AND ENDPOINTS**

**Table 4.-1: Objectives and Endpoints**

Objectives	Endpoints

Primary
 
To establish the tolerability of the combination of nivolumab and daratumumab in participants with advanced or metastatic solid tumors.
	
Incidence of adverse events (AE), serious adverse events (SAE) and specific laboratory abnormalities (worst grade).

Secondary
 
 
• To evaluate the objective response rate (ORR) of nivolumab combined with daratumumab in participants with advanced or metastatic tumors in each cohort.
 
• To assess progression free survival (PFS) of nivolumab combined with daratumumab in participants with advanced or metastatic tumors in each cohort.
 
• To characterize the pharmacokinetics of nivolumab and daratumumab in participants with advanced or metastatic tumors.
 
• To characterize the immunogenicity of nivolumab and daratumumab in participants with advanced or metastatic tumors
 
	
 
• ORR, duration of response (DOR), best overall response (BOR) in each cohort, based on RECIST 1.1 criteria (Appendix 7).
 
• Median PFS in each cohort
 
• Pharmacokinetic parameters, influence of intrinsic and extrinsic covariates and potential exposure-response relationship will be characterized using integrated analyses.
 
• Immunogenicity of nivolumab and daratumumab will be assessed by ADA positivity
 

[REDACTED]
 
[REDACTED]
 
[REDACTED]
	
[REDACTED]

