### 10.3.2 Safety Analyses

Safety analyses will be performed in all treated participants. Descriptive statistics of safety will be presented using NCI CTCAE version 4.0. All on-study AEs, treatment-related, AEs, SAEs and treatment-related SAEs will be tabulated using worst grade per NCI CTCAE v4.0 criteria by system organ class and MedDRA preferred term. On-study lab parameters including hematology, chemistry, liver function, thyroid function, and renal function will be summarized using worst grade per NCI CTCAE v4.0 criteria.

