LIST OF FIGURES

Figure 1.1-1: Study Design Schematic 6

Schedule of Analyses:

Interim analyses for futility were planned, separately for TNBC, NSCLC and PAC. Analyses were to be based on the first 20 participants of each cohort, after 4 months on treatment. The database lock (DBL) for the PAC interim was planned for Q2 2018; and for TNBC was anticipated for Q3 2018.

Under the circumstance that data of some tumor types mature faster than others or a strong signal was observed in some tumor types, additional interim analyses may have been performed prior to the completion of the study in order to facilitate program decisions such as expanding the current study or starting phase 3 development and to support presentations or publications.

Final analyses of each fully-accrued cohort was to be conducted, separately for each cohort.

On 13-June-2018, investigators were informed that Protocol CA209-9GW would be amended to allow single agent treatment of nivolumab for on-study participants with non-small cell lung cancer (NSCLC). In addition, only triple-negative breast cancer (TNBC) and pancreatic adenocarcinoma (PAC) participants who are deriving clinical benefit would continue to be treated with the nivolumab plus daratumumab combination therapy.

The enrollment of participants with NSCLC was closed due to the lack of an efficacy signal. This decision was not related to any serious adverse events associated with the use of nivolumab in combination with daratumumab. The enrollment of participants with TNBC and PAC was previously closed as the study had met enrollment goals in these 2 cohorts.

At that time, the protocol defined interim analysis was done after 20 patients treated for each cohort for both TNBC and PAC. The combination was discontinued before 20 patients were treated in the NSCLC cohort, thus the protocol defined interim analysis was not performed.

Following the decision of BMS to stop enrollment, only a final close out analysis will be performed at the end of the study. This statistical analysis plan describes these.

[figure not shown]

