6.3 Populations for Analyses

- All Enrolled subjects: All subjects who signed the informed consent form and obtained a subject number.
- All Treated subjects: All enrolled subjects who received at least one dose of any study treatment. This will be both efficacy and safety population.
- Subjects Entered Follow-up: All subjects who entered the follow-up period as specified in subject status CRF pages.
- All Treated Subjects with Objective Response: All treated subjects with response of CR or PR per RECIST v1.1 per Investigator.

Unless otherwise specified, the efficacy and safety analyses will include all treated subjects.

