7 STATISTICAL ANALYSES

7.1 General Methods

Unless otherwise noted, discrete variables will be tabulated by the frequency and proportion of subjects falling into each category, grouped by treatment. Percentages given in these tables will be rounded to the first decimal and, therefore, may not always sum to 100%. Percentages less than 0.1 will be indicated as '< 0.1'. Continuous variables will be summarized by treatment group using the mean, standard deviation, median, minimum, and maximum values.

Time-to-event variables (e.g. time-to resolution) will be analysed using the Kaplan-Meier technique. When specified, the median will be reported along with 95% CI using Brookmeyer and Crowley method¹ (using log-log transformation for constructing the confidence intervals²).

The conventions to be used for imputing missing and partial dates for analyses requiring dates are described in [Section 8](#).

All analyses would be presented by tumor type:

- Triple negative breast cancer (TNBC)
- Non-small cell lung cancer (NSCLC)
- Pancreatic adenocarcinoma cancer (PAC).

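### SAP 7.5.5 limits each laboratory test's population to subjects who already have the abnormality, so the laboratory part of the primary endpoint is no longer an incidence

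*SAP*

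**What the plan says.** Protocol Table 4.-1 gives the primary endpoint as "Incidence of adverse events (AE), serious adverse events (SAE) and specific laboratory abnormalities (worst grade"). Protocol 10.3.2 sets the population: "Safety analyses will be performed in all treated participants". The same paragraph covers the laboratory data: "On-study lab parameters including hematology, chemistry, liver function, thyroid function, and renal function will be summarized using worst grade".

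SAP 6.3 has a matching default: "Unless otherwise specified, the efficacy and safety analyses will include all treated subjects". SAP 7.5.5 then makes its own rule for laboratory tests: "The analysis population for each laboratory test is restricted to treated subjects meeting that laboratory test abnormality". SAP 7.1.2 counts each subject once per parameter at the worst on-treatment grade and names no denominator. SAP 7.1 requires percentages as well as counts: "discrete variables will be tabulated by the frequency and proportion of subjects falling into each category, grouped by treatment".

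The parameters for the worst-grade summary in SAP 7.5.5 begin "hemoglobin, hematocrit, leukocytes, platelet count, ALT, AST, alkaline phosphatase (ALP), total bilirubin". Neither absolute neutrophils nor absolute lymphocytes appear anywhere in that list.

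**The concern.** An incidence needs the people without the event in its denominator. The SAP 7.5.5 rule removes them, so the population for each test is defined by the outcome being measured. The printed percentage then describes how severity is distributed among affected subjects, not how often treated subjects are affected.

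This bears on a component of the primary endpoint. A reader of the report could take the percentages as tolerability rates and compare them between tests or between tumor cohorts. They would support neither use.

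The missing differential counts are a smaller matter of the same kind. Graded neutropenia or lymphopenia that nobody recorded as an AE could be absent from the laboratory summary.

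**Working it through.** **1. The plan's own safety figure.** Protocol 10.1 and SAP 5 say that 40 participants give more than 87% probability of seeing an event with a true rate of 5%.

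1 − 0.95^40 = 1 − 0.1285 = 0.8715, or 87.15%.

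The figure reproduces, with all 40 treated participants in the denominator.

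**2. Which rule governs.** The SAP 6.3 default gives way wherever another rule is specified, and SAP 7.5.5 specifies one. SAP 7.1.2 supplies no competing denominator, and SAP 7.1 means a percentage will be printed. The conflict with protocol 10.3.2 is therefore not resolved within the SAP.

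**3. Size of the distortion.** Let N be the subjects who belong in the denominator, k those with any grade of the abnormality, and g those at Grade 3-4.

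- Any grade: correct k/N; as written k/k = 100%.
- Grade 3-4: correct g/N; as written g/k.
- Inflation: (g/k) / (g/N) = N/k.

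N = 40 is the planned cohort size. The documents give no k or g, so these are assumed over a range.

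| k | g | Any grade, correct | Any grade, as written | Grade 3-4, correct | Grade 3-4, as written | N/k |
|---|---|---|---|---|---|---|
| 4 | 3 | 10.0% | 100% | 7.5% | 75.0% | 10.0 |
| 8 | 2 | 20.0% | 100% | 5.0% | 25.0% | 5.0 |
| 10 | 3 | 25.0% | 100% | 7.5% | 30.0% | 4.0 |
| 20 | 4 | 50.0% | 100% | 10.0% | 20.0% | 2.0 |
| 30 | 3 | 75.0% | 100% | 7.5% | 10.0% | 1.33 |

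The three rows with g = 3 have the same true Grade 3-4 rate and print as three different values.

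**4. Between cohorts.** The Schedule of Analyses in the SAP states: "The combination was discontinued before 20 patients were treated in the NSCLC cohort". That implies at most 19 treated in NSCLC at that time. With an assumed k = 4 in each cohort:

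- NSCLC: 4/19 = 21.1%, inflation 19/4 = 4.75.
- A cohort of 40: 4/40 = 10.0%, inflation 40/4 = 10.

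Both would print as 100%, hiding a twofold difference.

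**5. Threshold for an abnormality.** SAP 7.5.5 does not say what counts as meeting the abnormality; the table takes any grade. A stricter threshold only moves the problem: if it were Grade 3, then k = g and the Grade 3-4 rate would be g/g = 100%.

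**6. Neutrophils and lymphocytes.** Protocol Table 2.-2 schedules a blood count with differential at every hematology time point, and Table 9.4.4-1 lists the leukocyte count with its differential. SAP 7.5.5 lists leukocytes alone. Protocol 9.2.6 and 9.4.4 send laboratory abnormalities to the AE pages when they are clinically significant, serious, interrupt or stop treatment, or need corrective therapy. Protocol 7.1.1.1, 7.1.2.1 and 8.1.1 exempt certain grades of lymphopenia from delay, hold or discontinuation, so those cases need not reach the AE tables by the treatment-interruption route.

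**The case against.** The best defence is that nobody would choose a method that makes every any-grade rate 100%. The sentence is probably a slip for treated subjects with a result for the test. SAP 9 refers to a Data Presentation Plan with table mock-ups, not available here, whose shells may already use the right denominator. This bears on what was intended. It does not change what the SAP says, and no passage in either document supplies the intended reading.

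The reach is also limited, and this part stands:

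- The AE and SAE components of the primary endpoint are untouched.
- The hepatic and thyroid tables ask for numbers of subjects, which do not change.
- By-subject listings are required, so rates could be rebuilt by hand.
- The report is a synoptic close-out, and no decision rule uses these percentages.

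Rebuilding does, however, need the number tested, which SAP 7.5.5 does not ask for. The number treated is not a safe substitute: amylase and lipase are scheduled only for PAC participants, and free T3 and T4 are reflex tests.

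On the differential, the SAP list closely follows protocol Table 9.4.4-1, so leukocytes may be shorthand for the whole white-cell line, and SAP 7.1.2 mentions hematology in general. That reading is possible, which makes this part a request for clearer wording. Alone it would be a weaker point.

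**Conclusion.** The concern holds. As written, SAP 7.5.5 conditions the laboratory component of the primary endpoint on its own outcome and contradicts protocol 10.3.2. Any-grade incidence becomes 100% for every test with a case, whatever the counts. The inflation of grade-specific percentages is N/k; the 1.33- to 10-fold range above rests on assumed counts, the planned 40 per cohort, and reading the abnormality as any grade.

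The defect should be fixed before the tables are produced. It falls short of a fatal flaw because numerators, listings and the AE and SAE summaries survive. Confidence is high that the wording is wrong; whether wrong percentages would actually have been printed depends on table shells not seen here. The neutrophil and lymphocyte omission is accurate on the text and secondary.

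**What to change.** Replace the restricting sentence in SAP 7.5.5 with: *The denominator for each laboratory test is all treated subjects with at least one on-treatment result for that test.* Show the number tested per cohort for every parameter, beside the number treated, so that the table reconciles with the all-treated population in protocol 10.3.2.

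The number tested also handles the PAC-only tests, and it shows where there is little or nothing to summarise on treatment. Creatinine clearance, serology and FSH are marked as screening only in protocol Table 9.4.4-1, and urinalysis is scheduled only in Table 2.-1. The sponsor may wish to take these out of the on-treatment summary.

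Add absolute neutrophil count and absolute lymphocyte count by name to the worst-grade list. Check the mock-ups in the Data Presentation Plan against the new text.

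The cost is one sentence, one column and two parameter names. The data are already collected.
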